
Study n°	ABX464-401	Clinical Phase	2/3	
		Type of Study	Efficacy, Safety Study	
	
To assess the hospital stay duration in both treatment groups for patients hospitalized because of Covid-19 infection consequences compared to {Standard of care + placebo} treated group.
 
 – Number of days at the hospital from admission to discharge. 
To evaluate the effect of ABX464 on miR-124 expression in whole blood (PAXgene®) vs placebo (in selected sites and in hospitalized patients).
 
 – Change from baseline in microRNA-124 levels in total blood (PAXgene®) at D0, D7 and D28. 
To assess the change over time in CRP, Troponin I & T and D-dimer levels compared to {Standard of care + placebo} group.
 
 – AUC and % of change from enrolment in CRP, Troponin I & T and D-dimer levels. 
To evaluate the prevention of Covid-19 related deaths compared to {Standard of care + placebo} group
 
 – Time to death and mortality rate (all causes, and Covid-19 related). 
To evaluate the improvement in the 7-point ordinal scale during the course of the study compared to {Standard of care + placebo} group.
 
 – Time to improvement of one level in è-point ordinal scale. 
To evaluate SARS-CoV-2 infection in subjects during the course of the study compared to {Standard of care + placebo} group.
 
 – SARS-CoV-2 virus in nasopharyngeal sample and/or in blood at Day 0, 7 (hospitalized patients), 14, 21, and 28. 
To evaluate outpatients SpO₂ evolution from D0 to D14
 
 – Change in SpO₂ values from D0 to D14 in the outpatient's population. 
To evaluate the long-term effect of ABX464 on all cause mortality from first study drug intake to 3-months follow-up visit
 
 – Rate of participants deceased during the course of the study and follow-up, and time to event (in weeks). 
To evaluate the safety of ABX464 in study patients (from D0 to D48)
 
 – Number and rates of participants with Treatment Emergent Adverse Event – Cumulative incidence of serious adverse events (SAEs) including serious adverse drug reactions (SARs) and suspected unexpected serious adverse reactions (SUSARs) – Cumulative incidence of Grade 3 and 4 adverse events (AEs) – Number of participants with a discontinuation or temporary suspension of study drugs (for any reason) 
Exploratory criteria:
 
To assess the radiological findings for patients hospitalized because of Covid-19 infection consequences.
 
 – Central blinded review of the hospitalization discharge CT-Scans for descriptive analysis with regards to the disease severity and outcomes. 
To assess the long-term effect (4 months) of ABX464 on the respiratory function recuperation in patients having been hospitalized at least once throughout the study
 
 – Change from last dosing day in the Medical Research Council (MRC) dyspnea scale in the hospitalized patient's population according to treatment group. – Optional: Change from last dosing day in Pulmonary Function Tests (PFT) (Forced Expiratory Volume (FEV) and slow and forced Vital Capacity (VC)) and Carbon Monoxide Diffusing Capacity (CMDC) tests in the hospitalized patients population according to treatment group. 			

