2. STUDY OBJECTIVES AND ENDPOINTS

2.1. Primary objective and endpoint

The primary objective of the study is to determine the efficacy of ABX464 50mg to prevent respiratory failure or death in study patients.

- *Rate of patients who do not require use of high-flow oxygen (use of high-flow oxygen being defined as settings of 3 L/min or greater AND with at least one SpO₂ measurement < 92%, with or without O₂ supplementation) or, invasive or non-invasive mechanical ventilation (IMV and NIV, respectively) within 28 days and who are alive at the end of the 28 days period.*

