2.2. Secondary objectives and endpoints

The secondary objectives are:

To evaluate the proportion of patients requiring hospitalization during the study compared to the {Standard of care + placebo} group

- *Rate of patients hospitalized*

To assess the proportion of patients reporting each severity rating on a 7-point ordinal scale during the course of the study compared to the {Standard of care + placebo} group

- *Percentage of patients reporting each severity rating on a 7-point ordinal scale at each study visit (i.e. Not hospitalized, no limitations on activities; Not hospitalized, limitation on activities; Hospitalized, not requiring supplemental oxygen; Hospitalized, requiring supplemental oxygen; Hospitalized, on non-invasive ventilation or high flow oxygen devices; Hospitalized, on invasive mechanical ventilation or ECMO; Death);*

To assess the time to an improvement of one category of the 7-point on an ordinal scale from baseline, compared to the {Standard of care + placebo} groups

- *Change in the ranking on an ordinal scale from baseline to days 7, 14, 21, 28, 48 and at 4 months*

To evaluate and compare the effect of ABX464 on oxygen saturation before hospitalization

- *% change and AUC over time of oxygen saturation measured by daily pulse oximetry before hospitalization*

To evaluate and compare the effect of ABX464 on oxygen saturation level at the end of the study treatment

- *Rate of patients with SpO₂ ≤ 94% and rate of patients with SpO₂ ≤ 92% at Day 28*

To evaluate and compare the effect of ABX464 on immunophenotyping (in selected sites only) and cytokines levels during the study in patients enrolled in both treatment groups.

- *Change from enrolment in inflammatory markers in plasma (i.e. MCP-1, MIP-1 α , G-CSF, IL-1 β , IL-2, IL-6, IL-7, IL-10, IL-17, INF γ and TNF α) and in immune phenotype and assessment of cell-activation markers in PBMCs at D14, D28.*

To evaluate the proportion of patient requiring oxygen supplementation (>3L/min) during the study compared to the {Standard of care + placebo} group.

- *Rate of patients requiring oxygen supplementation*

To assess the time to hospitalization (all causes and Covid-19 related hospitalization) during the study compared to {Standard of care + placebo} treated group.

- *Time to hospitalization from baseline.*

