8. ADVERSE EVENTS (AE) AND SERIOUS ADVERSE EVENTS (SAE)

The investigator is responsible for the detection and documentation of events meeting the criteria and definition of an AE or SAE. During the study, in case of a safety evaluation, the investigator or site staff will be responsible for reporting AEs and SAEs, as detailed in this section of the protocol.

All adverse events (Serious and non-serious) will be collected from the time of signing of ICF and until D48 visit.

Any disease progression will be both reported in the eCRF as an adverse event and documented in the efficacy section.

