8.1.2. Definition of an Adverse Drug Reactions (ADR)

A response to a medicinal product which is noxious and unintended.

Suggesting that there is at least a reasonable possibility or suspicion of a causal relationship between the medicinal product and an adverse event.

8.1.3. Definition of a Serious Adverse Event (SAE) or Serious Adverse Drug Reaction (SADR)

A serious adverse event (experience) or reaction is any untoward medical occurrence that, at any dose:

a) Results in death

NOTE: Death is an outcome of an AE, and not an AE in itself. Event which led to death should be recorded with fatal outcome.

b) Is life-threatening

NOTE: The term 'life-threatening' in the definition of 'serious' refers to an event in which the patient was at risk of death at the time of the event. It does not refer to an event, which hypothetically might have caused death, if it were more severe.

c) Requires hospitalization or prolongation of existing hospitalization

NOTE: In general, hospitalization means that the patient has been detained (usually involving at least an overnight stay) at the hospital or emergency ward for observation and/or treatment that would not have been appropriate in the physician's office or out-patient setting. Complications that occur during hospitalization are AEs. If a complication prolongs hospitalization or fulfills any other serious criteria, the event is serious. When in doubt as to whether "hospitalization" occurred, or was necessary, the AE should be considered serious.

Hospitalization for Covid-19 infection consequences will be reported as a Serious Adverse Event.

Hospitalization for elective treatment of a pre-existing condition that did not worsen after informed consent was given is not considered serious.

d) Results in persistent or significant disability/incapacity,

NOTE: The term disability means a substantial disruption of a person's ability to conduct normal life functions. This definition is not intended to include experiences of relatively minor medical significance such as uncomplicated

headache, nausea, vomiting, diarrhea, influenza, and accidental trauma (e.g. sprained ankle) which may interfere or prevent everyday life functions but do not constitute a substantial disruption.

- e) Is a congenital anomaly/birth defect

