8.3. Events or Outcomes Qualifying as AEs or SAEs

8.3.1. COVID-19 related AE/SAEs

All COVID-19 related AE/SAEs will be recorded.

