4.11.2 Deaths, Serious Adverse Events, and Other Significant Adverse Events

Other significant adverse events are those adverse events reported as leading to an intervention e.g. withdrawal from study, discontinuation of study treatment, introduction of concomitant medication, dose reduction. Following the specification provided for adverse AE summaries at section 4.11.1 summaries detailed below will be provided for deaths, SAEs and other significant AEs:

- Number and percentage of patients for each TEAE leading to death, categorized by SOC and PT
- Number and percentage of patients for each treatment-emergent SAE, categorized by SOC and PT
- Number and percentage of patients for each TEAE leading to study discontinuation, categorized by SOC and PT
- Number and percentage of patients for each TEAE leading to treatment withdrawal, categorized by SOC and PT

For deaths, SAEs and other significant AEs the following listings will be provided:

- A by-patient listing of all deaths that occurred during the study
- A by-patient listing of all serious treatment-emergent adverse events
- A by-patient listing of all TEAE leading to treatment withdrawal
- A by-patient listing of all TEAE leading to study discontinuation

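### No planned table counts patients with serious or severe events other than COVID-19 progression, so the all-cause safety comparison can dilute or, if the drug works, offset an excess of other harm

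*Protocol*

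**What the plan says.** The safety objective (protocol synopsis and section 2.2, Day 0 to Day 48) is measured by, among others, "Cumulative incidence of serious adverse events (SAEs) including serious adverse drug reactions (SARs" and "Cumulative incidence of Grade 3 and 4 adverse events (AEs". Neither endpoint excludes COVID-19 events.

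The reporting rules put the disease under study into these counts:

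- Section 8: "Any disease progression will be both reported in the eCRF as an adverse event and documented in the efficacy section".
- Section 8.1.3: "Hospitalization for Covid-19 infection consequences will be reported as a Serious Adverse Event".
- Section 8.3.1: "All COVID-19 related AE/SAEs will be recorded".
- Section 8.2 removes only planned admissions or procedures and administrative or social admissions.

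The same events carry efficacy. Section 2.1 states: "The primary objective of the study is to determine the efficacy of ABX464 50mg to prevent respiratory failure or death in study patients". Section 2.2 lists "Rate of patients hospitalized" first among the secondary endpoints.

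For display, protocol 9.2 and SAP 4.11.1 plan an all-cause overview (any SAE, any grade 3 or higher event, SARs, SUSARs) and TEAE tables by organ class and preferred term, by grade and by relationship. SAP 4.11.2 adds "Number and percentage of patients for each treatment-emergent SAE, categorized by SOC and PT" and by-patient listings. SAP 5.0 removes every efficacy analysis after the futility stop (SAP 1 and 4.13) and leaves safety as the only objective in scope (SAP 2.2).

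**The concern.** An all-cause SAE comparison in this trial adds two quantities: serious COVID-19 worsening, which the drug is meant to reduce, and all other serious events, where unrelated harm would appear. At the planning rates the first is likely to be much the larger, so the total says little about the second.

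The planned breakdowns do not supply the missing number. Rows by organ class and preferred term count patients per term. A patient with two terms appears twice, so the rows cannot be added up to patients with at least one non-COVID SAE. The relationship, SAR and SUSAR rows depend on a causality judgement for each case. The protocol also describes that judgement in three ways: yes or no in 8.6, five categories in 8.7, and possible or probable in 9.2. In 8.7 the possibly-related category includes events that concurrent disease could explain.

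At stake is whether a reader of the overview table could see a moderate excess of other serious events. SAP 5.0 also drops the by-arm hospitalisation, ventilation and mortality analyses, which would have shown how much of the SAE total was disease progression.

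**Working it through.** **Inputs from the documents.** Planned response is 84% on ABX464 and 75% on placebo (protocol 9.5), so planned failure is q = 16% and 25%. Arm sizes are 533 and 267 (protocol 3.1). The documents give no expected SAE rate, so there is no SAE figure to reproduce. The one stated figure that rests on these rates is 78% power with 800 patients. Simulation with the futility look at 300 obeyed, no sample-size increase and unpooled variance gives 78.8%, so the planning rates are read correctly.

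**Assumptions not in the documents.**

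- f, the share of primary failures reported as SAEs: 1.0, 0.75 or 0.5. The product f × q stands in for the COVID-19 SAE rate.
- s, the risk of a non-COVID SAE: 3% on placebo, 9% on ABX464.
- The two kinds of event are independent.

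**Formulas.** All-SAE risk = 1 − (1 − f·q)(1 − s). Difference = ABX464 minus placebo, with a Wald 95% CI: difference ± 1.96 × √[pA(1 − pA)/533 + pP(1 − pP)/267].

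**A. Drug works as planned (16% vs 25% failure).**

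| f | Placebo | ABX464 | Difference, points (95% CI) |
|---|---|---|---|
| 1.0 | 1 − 0.75 × 0.97 = 27.25% | 1 − 0.84 × 0.91 = 23.56% | -3.7 (-10.1 to +2.8) |
| 0.75 | 1 − 0.8125 × 0.97 = 21.19% | 1 − 0.88 × 0.91 = 19.92% | -1.3 (-7.2 to +4.7) |
| 0.5 | 1 − 0.875 × 0.97 = 15.13% | 1 − 0.92 × 0.91 = 16.28% | +1.2 (-4.2 to +6.5) |

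**B. Drug has no efficacy (25% failure in both arms, f = 1.0).** Placebo 27.25%; ABX464 1 − 0.75 × 0.91 = 31.75%. Difference +4.5 points. Standard error = √(0.3175 × 0.6825/533 + 0.2725 × 0.7275/267) = 3.39 points, so the CI is -2.1 to +11.1.

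**C. Non-COVID SAEs counted separately.** 9% − 3% = +6.0 points. Standard error = √(0.09 × 0.91/533 + 0.03 × 0.97/267) = 1.62 points, so the CI is +2.8 to +9.2. This result does not depend on f or on efficacy.

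**Break-even under A.** The excess of non-COVID SAEs that leaves the all-SAE rates equal is (1 − s) × [1 − (1 − 0.25f)/(1 − 0.16f)], with s the placebo risk. At s = 3% this is 0.97 × (1 − 0.75/0.84) = 10.4 points for f = 1.0, and 0.97 × (1 − 0.875/0.92) = 4.7 points for f = 0.5.

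**Reading.** The assumed 6-point excess is offset in A and diluted in B. In all four all-cause comparisons the interval includes zero, while the separated interval excludes it. The standard error also roughly halves, from 3.39 points in B to 1.62 in C, because COVID-19 events no longer add variance.

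**The case against.** The strongest reply is that all-cause SAE reporting with breakdowns is standard and that the plan already has several ways to see other harm. SARs and SUSARs have their own overview rows. Every grade 3 or higher event goes to the DSMB within 24 hours for causality assessment (protocol 3.2 and 3.3). Laboratory shift tables are planned. In the illustration, 9% of 533 is about 48 patients against 3% of 267, about 8; a difference of that size would hardly pass unnoticed in term-level tables and listings. The protocol also planned COVID-19-related versions of time to hospitalisation and of mortality.

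Much of this stands: the plan does not conceal such events. But term-level rows give no patient total, the SAP does not say that its relationship tables use the DSMB's assessment, and SAP 5.0 dropped the COVID-19-specific hospitalisation and mortality analyses.

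Two stronger readings are tempting and are not supported:

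- *The all-SAE row would make a harmful drug look safer.* That needs both a real benefit and a large share of failures reported as SAEs. At f = 0.5 the difference already points towards harm, and the futility stop recorded in SAP 1 and 4.13 makes a benefit of the planned size unlikely.
- *Lack of efficacy would look like toxicity.* In a placebo-controlled comparison an inactive drug leaves COVID-19 SAEs equal in expectation. They add noise. A true excess would mean that the drug worsened COVID-19, which is itself harm.

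**Conclusion.** The point holds as a gap in the planned safety tables. Serious and severe events are summarised across all causes, COVID-19 progression must be included, and no table gives the by-arm patient count without it. The effect is dilution if the drug does nothing and offsetting if it works. With assumed non-COVID SAE rates of 3% and 9%, a separated difference of +6.0 points appears as anything from -3.7 to +1.2 under the planned efficacy, depending on f, and as +4.5 with a CI including zero under no efficacy at f = 1.0.

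The direction follows from the text. The sizes are illustrative: they rest on f, on the assumed non-COVID rates, on independence and on the full planned enrolment, which a trial stopped early need not have reached. Separation does not cure low power either. For 3% against 6%, power with 267 and 533 patients is only about 45% (two-sided 0.05).

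A reader might infer that the safety conclusion should rest on non-COVID events alone. The documents do not support that. ABX464 acts on inflammation in patients with an active infection, and SAP 5.0 contains no efficacy analysis. Drug-worsened COVID-19 would then enter no conclusion at all.

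**What to change.** In protocol 9.2 and SAP 4.11.1 and 4.11.2, keep the any-SAE and grade 3 or higher rows as they are. For each, add two by-arm counts of patients with at least one event:

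- (a) COVID-19 progression events, defined by a preferred-term list fixed before unblinding;
- (b) all other events.

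State that the all-cause row, (a) and (b) will be interpreted together, so that any drug-related worsening of COVID-19 stays visible in (a).

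The cost is one blinded term list and a few table rows. No new data are needed, because section 8.3.1 already has COVID-19-related events recorded, and the pre-unblinding meeting in SAP 4.6 is a natural place to agree the list. The small downside is that some events will be hard to classify, which is a further reason to keep the all-cause rows beside the split.

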1. INTRODUCTION AND STUDY RATIONALE

1.1. SARS-CoV-2 infection

Coronaviruses are a large family of viruses that are known to cause illness ranging from the common cold to more severe diseases such as Middle East Respiratory Syndrome (MERS) and Severe Acute Respiratory Syndrome (SARS).

A novel coronavirus SARS-CoV-2 (previously known as 2019-nCoV) was identified in 2019 in Wuhan, China. This is a new coronavirus that has not been previously identified in humans. The precise etiology is unknown and therefore medical therapy to cure the disease is not yet available.

The coronavirus disease 2019 (COVID-19) is an acute respiratory disease caused by this novel coronavirus, that shows sustained human-to-human transmission, and has been exported around the globe to reach pandemic proportion (1). The World Health Organization (WHO) officially declared the COVID-19 pandemic as a public health emergency of international concern. The novel coronavirus uses the same cell surface receptor, angiotensin-converting enzyme 2 (ACE2) as SARS-CoV, for entry, and infects preferentially the respiratory tract where this receptor is expressed (2). The elderly and people with underlying diseases are most prone to serious outcomes, which appear to be associated with acute respiratory distress syndrome (ARDS) and cytokine storm syndrome (1).

1.2. Management of patients

Two therapeutic strategies are currently being explored:

- To limit the spread of the COVID-19 infection by blocking the replication of the virus. This may be achieved through inhibition of the viral RNA dependent polymerase (RdRp) or by preventing the entry of the virus into pulmonary target cells or by serotherapy using immunized patient's plasma,
- To dampen the body's inflammatory response in the pulmonary tract.

Antiviral drugs for managing infection with human coronaviruses are not yet approved, posing a serious challenge to current global efforts aimed at containing the outbreak of COVID-19. Companies, including Gilead and AbbVie, are testing antiviral combination therapy, especially nucleoside analogues to block RdRp, and protease inhibitors in clinical trials, in order to block the entry of the virus into cells. Chloroquine is being evaluated based on its ability to block viral processes and maturation.

Several companies, including Sanofi, Abbvie, Roche/Genetech, are testing monoclonal antibody therapy to block the inflammatory response by inhibiting individual inflammatory receptor pathways.

Additional therapies focused on thromboembolic complications and standard intensive care treatments are also being studied.

The response to each of these therapies is highly uncertain and, given the scope of this pandemic, other treatment options that more broadly target the immune "Cytokine Storm" syndrome must urgently be explored in well-designed clinical trials.

1.3. Study rationale

Developed initially as an inhibitor of HIV replication (3-5) and HIV reservoir reduction (6), ABX464 binds to the Cap Binding Complex (CBC) that regulates splicing and export of mRNA from the nucleus (3). ABX464-CBC interactions were shown to strengthen the RNA quality control of HIV-RNA biogenesis preventing the production of unspliced HIV RNA (3), thereby reducing the viral reservoirs of HIV infected patients (6).

While capable of directly altering the splicing of ~0.1% of transcripts in cells, the examination of the effects of ABX464 on the microRNA population using the Affymetrix Genechip microRNA array 2.0, and a TaqMan® Array Human microRNA for confirmation, showed that the selective expression of a single microRNA was significantly increased by ABX464: miR-124 (7).

MicroRNAs are small noncoding RNAs that regulate gene expression by binding to the 3' UTR of their target mRNAs to induce translational repression and mRNA deadenylation and decapping (8). As a result, microRNAs reduce expression of target genes by increasing degradation of the respective RNA and/or inhibiting their translation into proteins. Often, microRNAs regulate sets of genes belonging to the same pathway.

[figure not shown]
miR-124 is transcribed from 3 genomic loci, locus 1 (exonic), locus 2 (monocistronic) and locus 3 (monocistronic). Studies have demonstrated that ABX464 induces miR-124 expression from locus 1 only. Locus 1 contains the long

non-coding RNA, lncRNA00599-205 from which miR-124 is derived by splicing. Mutation of the splice sites of lncRNA00599-205 prevented the overexpression of miR-124 with ABX464 treatment (7).

The RNA targets of miR-124 have been shown to be related to the cytokine and pro-inflammatory response of innate immune cells, especially tissue-resident macrophages. The JAK-STAT pathway that is downstream of cytokine signaling is affected by miR-124, especially STAT3 (9), as is NFkB, the master transcription factor of pro-inflammatory responses (10). In addition, miR-124 has been shown to have a direct effect on the translational downregulation of MCP-1, monocyte chemoattractant protein (11), as well as the IL-6 receptor (10). In conjunction with these effects, the increase of miR-124 has been associated with the maintenance of the M2 differentiation of the tissue-resident macrophage. Indeed, M2 macrophages control tissue inflammation by producing type 2 cytokines such as IL-4 and IL-10, two mediators of tissue homeostasis (12). In summary, miR-124 is anti-inflammatory by reducing protein levels of these pro-inflammatory pathways, and also anti-proliferative by affecting some of the important cell cycle transcripts (10).

In the mouse model of Dextran Sodium Sulphate (DSS) exposure in which colonic inflammation is triggered, ABX464 demonstrated a marked decrease in the inflammatory colitis (13, 14). This effect was associated with prevention of proliferation of Th17 cells in both peripheral blood and mesenteric lymph nodes. Th17 cells, the CD4+ T-cell subset that produces interleukin-17 (IL-17) and are pro-inflammatory and are dependent on STAT3 for proliferation (15, 16). IL-17 is a highly inflammatory cytokine with robust effects on stromal cells in many tissues. ABX464 showed also efficacy in animal models related to rheumatoid arthritis (CIA mice model) as well as a good bioavailability in lung tissues.

In addition, a reduction of SARS-CoV-2 replication in an *in-vitro* reconstituted human airway epithelial model showed comparable efficacy between remdesivir (5µM) and ABX464 (0.1, 1 and 5µM).

Based on Day 1 human PK plasma data (C_{max}) for ABX464, the concentration range used in this assay is achievable in human using the 50mg QD dose. The mean C_{max} of ABX464 is approximatively 0.2µM. Furthermore, from the radiolabelled rat study (cf current version of IB), ABX464 is known to distribute in the whole body leading to a favourable exposure in lung tissue as presented in the table below.

	1 hour	4 hours	8 hours	24 hours
Plasma *	0.461	1.25	1.18	0.203
Lung	1.19	1.89	1.45	0.457

Numbers are in µg equivalents/g for all measurements. Concentrations of radioactivity in tissues of male albino rats after a single oral administration of [¹⁴C]-ABX464 at a nominal dose level of 20mg/kg body weight

